## ***3.2 Allocation to Interventional Group***

After completing the baseline survey, all caregivers will be randomized into one of two groups: 1) TCBD intervention group, or 2) control group. Computerized, block randomization (block sizes from four to eight) will be applied to assign eligible caregivers to the TCBD intervention or control group in a 3:1 ratio. Blocks will be stratified by age groups related to child passenger safety recommendations (<2 years – rear-facing CRS, 2-4 years – forward-facing CRS, 5-10 years – booster seat) and the child passenger safety behavior that led to eligibility for study (not using the recommended restraint currently or planning a premature transition in the coming 6 months).

After the 6-month follow-up assessment, caregivers in the intervention group only who continue suboptimal CRS use will be re-randomized by computer in a 1:1 ratio to receive either the basic or enhanced intervention. The enhanced TCBD will include one additional motivational interviewing (MI) session by phone in Month 7/8 and one to two additional tailored text messages in Months 7-12 (total of 7 tailored tips during these months compared to 4 tailored tips for those in the basic TCBD). The extra text messages will be sent to those in the enhanced TCBD group until size-appropriate restraint use is observed. Caregivers receiving enhanced TCBD will be encouraged to obtain a free seat check with a certified child passenger safety technician (CPST) in the community. The primary outcomes (size-appropriate CRS use and CPaSS) will be assessed in-person at Months 6 and 12. The secondary outcome, the CPaSS trajectory, is a measure of correct and consistent restraint use in response to the intervention and will be assessed by scoring photographs submitted by caregivers (Months 1-5; 7-11).

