### 4.2 Total Number of Subjects and Sites

To test the Tiny Cargo, Big Deal Intervention, we anticipate the need to screen 10,000 caregivers to recruit 900 caregivers who will be enrolled in the study and randomized to intervention or control. All recruitment will occur in the Emergency Department (ED) at Lurie Children's Hospital of Chicago (LCH) or remotely via phone/email/text message. With this most recent IRB modification (3/26/21), we will also add recruitment via flyers in patient treatment rooms from Lurie Children's affiliate EDs (e.g., Central DuPage, Northwest Community) and Lurie Children's Immediate Care Centers (Lincoln Park and Northbrook).

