## 6 Statistical Plan

### 6.1 Sample Size and Power Determination

Briefly, our calculations are based on two-sample comparisons between groups (e.g., control and TCBD) using results from our pilot study that assessed percent size-appropriate child passenger safety behaviors at 6-month follow-up (referred to as the “response rate” below). For analyses involving multiple time points, these calculations represent a conservative lower bound on the power that would only be achieved if the effective sample equals 1 observation per person (i.e. perfect within-individual correlation). For the calculations below we assume: a) 17% response rate among controls; b) 25% response rate among TCBD caregivers at 6 Month (with 75% of TCBD caregivers re-randomized); and c) only 80% of the target sample (n=204 controls and n=516 TCBD in the initial dichotomy) will be available for analysis at follow-up. Components (a) and (b) are based on pilot data where the control group received generic educational materials and outcomes were assessed at 6-months. Component (c) is a conservative correction for attrition. For Aim 2, we estimated power while accounting for uncertainty in the group sizes by simulating response and re-randomization patterns according to the above probabilities and testing for significant between-group differences; this process was repeated 10,000 times and the power was estimated as the percent of replications in which a between-group difference was identified. Binary Outcome: For the binary response case, if the observed response rate is at least 29.4% among those receiving enhanced TCBD, it can be reliably (>80% power) distinguished from a control response rate of 17%. Analogously, a response rate of at least 27.6% among basic intervention would be reliably (>80% power) distinguished from control. Converted to Cohen's  $h$ , both differences reflect small-to-medium effect sizes ( $h = 0.30$  and  $h = 0.26$ , respectively). Numeric Outcome (CPaSS): If the standardized mean difference (i.e. Cohen's  $D$ ) is  $>0.25$  (a small-to-medium effect size), we can reliably distinguish between control and basic TCBD conditions. Similarly, if  $D \geq 0.28$ , a small-to-medium effect size, we will have sufficient power (80%) to distinguish the control and enhanced TCBD conditions. Aim 2: Monte Carlo studies of linear latent trajectory models indicate that a medium level of heterogeneity among the slopes and/or intercepts of the trajectories can be reliably recovered (power  $> 80\%$ ) with a total sample size of  $n=200$ , with power exceeding 95% when the level of heterogeneity is high; given that our sample size soundly exceeds 200, we expect sufficient ability to determine the underlying characteristic trajectory types. Nevertheless, we further justify our sample size with a brief simulation study. Assuming a final sample size of 720, conservatively assuming individuals are only measured at an average of 25% of the 12 monthly assessments, we simulate data from a population with four equally likely trajectory types: consistently low, consistently high, linearly decreasing, and starting high then dropping off. Because we have no basis for estimating variability in the score, we assumed mean/variance equivalence, consistent with the Poisson distribution. Due to the time required to fit such models, we only completed 200 simulation replications, where we were able to correctly conclude (based on BIC) that there were four

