## 6.2 Statistical Methods

All subjects, once randomized, will be included in an intention-to-treat analysis and outcomes will be collected even if the caregiver does not engage in the randomly assigned intervention. We will evaluate randomization by testing for covariate (e.g. demographic characteristics) balance between initial treatment groups, and between the re-randomized treatment groups created after the 6-month follow-up. If significant differences are observed, we will adjust for these variables or conduct stratified analyses. All statistical hypothesis tests and power calculations will use a two-sided = 0.05.

**Aim 1:** To test the efficacy of the TCBD intervention compared to usual care for improving primary outcomes [i.e., size-appropriate restraint (dichotomous) and CPaSS (numeric)] at 12 months. We hypothesize greater proportions of children will be using a size-appropriate restraint and higher CPaSS among caregivers in the intervention groups (basic and enhanced) compared with the control group (usual care) at the 12-month assessment. **Statistical Analysis:** Our primary analytic tool for estimating treatment effects will be generalized linear models (GLMs), and for analyses involving joint analysis of multiple follow-up data points, we will use generalized linear mixed models (GLMMs), which allows direct modeling of the correlations between data points (e.g. repeated measurements on individuals), and the inclusion of individuals with incomplete data (e.g. missing time points). The GLM(M) framework also allows simple controlling for confounders (if necessary) through their inclusion in the model as covariates. For the analysis of binary outcomes, we will use logistic GLM(M)s and for numeric outcomes (CPaSS-D) we will initially specify linear (Gaussian) GLM(M)s; this choice will be scrutinized by analyzing model diagnostics. The primary inferential target will be the coefficient for the treatment group indicator, making this effectively equivalent to ANCOVA. Adjustment for the baseline measurement is important for guarding

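### No enhanced-versus-basic comparison on the two primary outcomes is specified or powered for the caregivers re-randomised at Month 6

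*Combined protocol and SAP*

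**What the plan says.** All references are to the combined protocol and SAP.

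- **Design.** Section 1.1 lists a second, more intense level for caregivers who have not changed by Month 6 as one of four features of the intervention. Under 3.2, intervention-arm caregivers whose restraint use is still suboptimal after the Month 6 assessment "will be re-randomized by computer in a 1:1 ratio to receive either the basic or enhanced intervention".
- **Aim 1 hypothesis (6.2).** More size-appropriate restraint use and "higher CPaSS among caregivers in the intervention groups (basic and enhanced) compared with the control group (usual care) at the 12-month assessment". The inferential target is the coefficient of a treatment-group indicator whose levels are not defined.
- **Aim 1 power (6.1).** There are four detectable effects: 29.4% (enhanced) and 27.6% (basic) against 17% in controls, and D of 0.28 (enhanced) and 0.25 (basic). All are against control. For enhanced on CPaSS, for example, "we will have sufficient power (80%) to distinguish the control and enhanced TCBD conditions".
- **Costs (2.2 and 6.1).** Net cost is basic minus control and enhanced minus control.
- **Re-randomised groups (6.2).** The only analysis that names them as such is a check of covariate balance.
- **Aim 2 (6.2).** CPaSS trajectories are expected to differ across basic, enhanced and control. Treatment group is one of the correlates in a multinomial model of trajectory class.

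**The concern.** The Month 6 randomisation protects one comparison: enhanced against basic, among the caregivers who were re-randomised. The plan does not name that comparison for size-appropriate use or for CPaSS, and gives it no power figure.

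The planned comparisons cannot stand in for it. Enhanced contains only Month 6 non-responders. Basic, as powered, also contains every Month 6 responder. Comparing the final groups, directly or each against control, therefore mixes the effect of the enhancement with selection on the Month 6 outcome.

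Anyone deciding whether to adopt the second level will ask what the extra phone session and texts add. Without a prespecified contrast the answer will be post hoc, with population, covariates and outcome open to choice.

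**Working it through.** **Inputs**

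- Significance level (6.2): "All statistical hypothesis tests and power calculations will use a two-sided = 0.05".
- Control rate (6.1): "a) 17% response rate among controls".
- Month 6 response (6.1): "25% response rate among TCBD caregivers at 6 Month (with 75% of TCBD caregivers re-randomized".
- Analysable sample (6.1): "only 80% of the target sample (n=204 controls and n=516 TCBD in the initial dichotomy) will be available for analysis at follow-up".
- Enrolment (4.2): "recruit 900 caregivers who will be enrolled in the study and randomized to intervention or control"; 80% of 900 = 720 = 204 + 516.

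**Step 1: group sizes**

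- Re-randomised: 0.75 × 516 = 387, or 193.5 per group.
- Month 6 responders: 516 − 387 = 129.
- Final basic group with responders included: 193.5 + 129 = 322.5.
- The 3:1 ratio in 3.2 would instead split 720 as 540:180, so 0.75 × 540 = 405, or 202.5 per group.

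**Step 2: reproduce the plan's figures**

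For means, detectable D = (1.960 + 0.842) × √(1/n₁ + 1/n₂).

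- Enhanced v control: 2.802 × √(1/204 + 1/193.5) = 0.281 (plan: 0.28).
- Basic v control: 2.802 × √(1/204 + 1/322.5) = 0.251 (plan: 0.25).

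For proportions (two-sample test, pooled variance under the null):

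- Enhanced, 29.4% v 17%, n = 193.5 and 204: power 83.7% (80.5% with continuity correction).
- Basic, 27.6% v 17%, n = 322.5 and 204: power 80.9% (77.8% corrected).
- Basic with only the 193.5 re-randomised to it: power 72.1%.

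Both basic figures need about 322 in the group. Basic as powered therefore includes the Month 6 responders.

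**Step 3: what final-group comparisons would show if the enhancement did nothing**

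Suppose nobody changes after Month 6.

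- Basic: 129/322.5 = 40%.
- Enhanced: 0/193.5 = 0%.
- Whole TCBD arm: 129/516 = 25%.

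Against a 17% control rate, basic would look 23 points better and enhanced 17 points worse, with no enhancement effect at all. The case is extreme, but it shows the direction of the distortion.

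**Step 4: precision of the restricted contrast**

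- CPaSS: 2.802 × √(2/193.5) = 0.285; with 202.5 per group, 2.802 × √(2/202.5) = 0.278.
- Binary: the documents do not give the Month 12 rate among caregivers re-randomised to basic, so the rates below are assumptions.

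| Assumed basic rate | Enhanced rate needed, 193.5 per group | Enhanced rate needed, 202.5 per group |
|---|---|---|
| 5% | 13.2% | 12.9% |
| 10% | 20.2% | 19.9% |
| 17% | 28.9% | 28.7% |
| 25% | 38.2% | 37.9% |

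On CPaSS this is almost the precision that 6.1 already accepts for enhanced against control.

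**The case against.** **Aim 2 covers it.** A reader of Aim 1 alone might infer that every hypothesis and power figure is against control and that the second randomisation tests nothing. The documents do not support that. Aim 2 expects basic, enhanced and control to differ and models trajectory class on treatment group. Its power figures (n = 200 for trajectory heterogeneity; a simulation with 720 caregivers) concern recovery of classes, not a difference from control. Section 6.1 also mentions simulating re-randomisation and testing between-group differences, without limiting these to control. But Aim 2 does not fill the gap. Its outcome is secondary, its trajectories include Months 1–5, it is not restricted to re-randomised caregivers, and it states no pairwise contrast. Enhanced would differ from a mixed basic group on selection alone.

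**The data will exist.** One might also infer that the trial cannot evaluate the second level. That goes too far: allocation is random and 1:1, analysis is by intention to treat, outcomes are collected regardless of engagement, and Month 12 is assessed for everyone. What is missing is the prespecified contrast.

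**It is not a stated objective.** This is correct. The primary aim is TCBD against usual care, and the omission does not by itself bias that comparison. This limits the severity.

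**The binary test may be inconclusive.** This stands. At assumed basic rates of 10% to 17%, the detectable gain is about 10 to 12 points. That exceeds the 25 − 17 = 8 points assumed for TCBD against control at Month 6.

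**The cost difference follows by subtraction.** The control mean cancels, but the result compares enhanced with a basic group that includes responders. As the cost analysis is exploratory, a restricted version is optional.

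**Conclusion.** The gap is real and should be fixed: neither primary outcome has a specified or powered enhanced-versus-basic contrast restricted to the re-randomised caregivers. It does not invalidate the primary comparison with usual care.

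The sizes rest on 6.1's assumptions of 75% non-response at Month 6 and 720 analysable caregivers, with the 75% applied to the analysable TCBD arm. The binary thresholds rest in addition on an assumed rate for re-randomised basic, and a modest binary effect could be missed.

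A reader might also infer that the first-stage allocation was tilted towards TCBD mainly to feed the second stage. The documents give no reason for the ratio. They also state it inconsistently, since 516:204 is about 2.5:1 and not 3:1, so nothing here depends on that reading.

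**What to change.** 1. **Section 6.2:** add a key secondary analysis, placed below the primary, of enhanced versus basic among re-randomised caregivers only, analysed as re-randomised. Outcomes: size-appropriate use and CPaSS at Month 12. Adjust for Month 6 CPaSS and the original stratification factors. Month 6 CPaSS is a usable covariate because Month 6 size-appropriate use is the same for everyone in this set.
2. **Section 6.1:** state the precision: about 194 per group (203 at a true 3:1 split), detectable D about 0.28 at 80% power, and the binary thresholds with the assumed basic rate labelled as such. Reconcile 516:204 with the 3:1 in 3.2.
3. **Optional:** report the enhanced-minus-basic cost in the same set.

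The cost is SAP wording and one extra analysis, with no new data or participants. The downside is one more named comparison. The text should be settled before Month 12 outcomes are examined by re-randomised group.

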# Emergency Medicine Prospective Protocol

against regression to the mean in RCT studies, which will be our approach when analyzing only a single follow-up (e.g. 12 months). However, when analyzing multiple follow-ups within the same model, using this baseline adjustment across the board (i.e. at every time point) can result in overestimation of the treatment effect; baseline adjustment for only the first follow-up corrects this overestimation while also guarding against regression to the mean, which will be our approach. We will also conduct exploratory tests of the interaction between time and treatment group, to see whether there is strong evidence that the treatment effect diminishes over time, which will inform future studies.

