**Aim 2:** To use latent growth curve models to identify characteristic trajectories for the CPaSS observed in digital photographs over the 12 study months and assess for correlates of the trajectory types. We hypothesize that caregivers will have different CPaSS trajectories in response to the basic intervention, the enhanced intervention, and the control condition. We expect to identify at least four patterns of response. **Statistical Analysis:** We will determine 12-month CPaSS trajectory types using adaptations of finite mixture models for the case where the units are trajectories. We will define trajectory shapes through methods combining semiparametric regression modeling (e.g., generalized additive models), with latent class regression, using the R package flexmix. Following convention, we will use the Bayesian Information Criteria (BIC) to determine the appropriate number of latent classes, while also making practical considerations to avoid overfitting, such as not allowing overly small groups to be created, as in previous applied work. Using the posterior probability of class membership, we place individuals into trajectory groups and treat that grouping as the outcome in a subsequent multinomial regression model to determine correlates of class membership, including treatment group, caregiver race/ethnicity, and child age group. If substantial uncertainty in class membership is found, outcomes in the multinomial model will be weighted accordingly.

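### Section 6.1 powers basic v control and enhanced v control on groups formed by Month-6 response, and 6.2 does not say whether the Aim 1 indicator is that biased split or the initial arm

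*Combined protocol and SAP*

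**What the plan says.** Under 3.2, caregivers are first randomised to TCBD or control. After the Month-6 assessment, "caregivers in the intervention group only who continue suboptimal CRS use will be re-randomized by computer in a 1:1 ratio" to basic or enhanced TCBD. Month-6 responders in the TCBD arm simply continue on basic. Controls are never divided by Month-6 status.

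Section 6.1 assumes 17% response in controls, 25% response in TCBD at Month 6 (so 75% re-randomised), and 204 controls and 516 TCBD caregivers available for analysis. It then gives separate detectable effects. For enhanced TCBD: "if the observed response rate is at least 29.4% among those receiving enhanced TCBD, it can be reliably (>80% power) distinguished from a control" rate of 17%. For basic TCBD: "a response rate of at least 27.6% among basic intervention would be reliably (>80% power) distinguished from control". For CPaSS the corresponding standardised differences are 0.25 (basic) and 0.28 (enhanced). It states no detectable effect for TCBD as a whole against control.

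Section 6.2 frames the Aim 1 hypothesis as a benefit "among caregivers in the intervention groups (basic and enhanced) compared with the control group (usual care) at the 12-month assessment". It specifies GLMs or GLMMs, adjusts a single-follow-up analysis for baseline, and says: "The primary inferential target will be the coefficient for the treatment group indicator". Balance checks are planned "between initial treatment groups, and between the re-randomized treatment groups created after the 6-month follow-up", so both sets of groups are in view, but the text does not say which set defines the indicator. No weights are given.

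**The concern.** Basic and enhanced are not randomised alternatives to control. Membership depends on the Month-6 value of a primary outcome: enhanced contains only caregivers who were failing at Month 6, and basic is enriched with everyone who was succeeding. Against unselected controls, basic will look too good and enhanced too bad, unless Month-6 restraint use says nothing about Month-12 use in the same family.

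The primary contrast can therefore be read in two ways. As initial TCBD arm v control it is valid but has no stated power. As basic v control and enhanced v control it is what 6.1 powers, but it can show benefit for basic and harm for enhanced when neither does anything. An undefined indicator also leaves the choice open until the data are seen. The same ambiguity reaches Aim 2, whose hypothesis is that "caregivers will have different CPaSS trajectories in response to the basic intervention, the enhanced intervention, and the control condition", and the cost comparisons by basic and enhanced group.

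**Working it through.** **1. Which groups does 6.1 power?** Inputs from 6.1: 516 TCBD, 204 control, 25% responders at Month 6, two-sided 5% test (6.2), 80% power. The 1:1 re-randomisation is from 3.2.

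- Responders: 516 × 0.25 = 129. Non-responders: 387, or 193.5 per re-randomised group.
- Enhanced = 193.5. Basic = 129 + 193.5 = 322.5, of whom 129/322.5 = 40% are responders.
- Detectable D = (1.96 + 0.84) × √(1/n + 1/204):
  - basic, n = 322.5: 0.251 (plan: 0.25)
  - enhanced, n = 193.5: 0.281 (plan: 0.28)
  - an even split, n = 258 each: 0.262 for both
- Power for 27.6% v 17% (pooled-variance z test): 80.9% with basic = 322.5, 77% with 258, and 72% with 193.5 (re-randomised non-responders only). Only the first agrees with the plan's claim of more than 80%.
- Power for 29.4% v 17% with enhanced = 193.5: 83.7%, consistent with more than 80%.

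**2. Bias when nothing works, unadjusted.** Let 17% respond at both visits in everyone, with no effect of basic or enhanced. Let *a* be the share of Month-6 responders who still respond at Month 12. The documents give no value for *a*, so it is varied. Non-responders then respond at Month 12 at rate b = 0.17(1 − a)/0.83. With 17% responding at Month 6, responders make up 0.17 and basic non-responders 0.415 of the TCBD arm, so:

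- expected basic rate = (0.17a + 0.415b)/0.585
- expected enhanced rate = b

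For a = 0.5: b = 0.085/0.83 = 10.2%, and basic = (0.085 + 0.0425)/0.585 = 21.8%, against 17% in control.

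Simulation of 100,000 trials per row at 516/204, pooled-variance z tests:

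| Persistence *a* | Basic rate | Enhanced rate | Basic falsely better | Enhanced falsely worse |
|---|---|---|---|---|
| 17% (independence) | 17% | 17% | 2.3% | 2.5% |
| 30% | 19% | 14% | 8% | 11% |
| 50% | 22% | 10% | 26% | 53% |
| 60% | 23% | 8% | 40% | 78% |
| 70% | 25% | 6% | 55% | 95% |

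The nominal rate in each of the last two columns is 2.5%. Pooled TCBD v control stays at about 5% two-sided in every row. Weighted strategy contrasts with robust standard errors give 5.1–5.2%.

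**3. With the plan's baseline adjustment.** Logistic model adjusted for baseline, 4,000 trials per scenario. Responses come from latent normal variables with 20% or 40% correct at baseline. These baseline rates and the latent correlations are assumptions. Latent Month-6 to Month-12 correlations of 0.3, 0.5 and 0.7 correspond to persistence of about 30%, 41% and 54%.

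| Persistence | Basic falsely better | Enhanced falsely worse |
|---|---|---|
| 30% | 6–7% | 9% |
| 41% | 10–11% | 18–19% |
| 54% | 14–29% | 33–60% |

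The range in the last row reflects how strongly baseline predicts follow-up (latent correlation 0.7 down to 0.3). The adjusted pooled test gives 4.6–5.7% two-sided.

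**4. Power of the valid contrasts, at 516/204.**

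- Pooled TCBD v control: D = 2.80 × √(1/516 + 1/204) = 0.232; detectable rate about 26.7% v 17%. Power for the plan's own 25% v 17% is 64.5%.
- Each weighted strategy: effective n = 516²/(129 × 1² + 193.5 × 2²) = 266,256/903 = 295; D = 0.255; detectable rate about 27.7% v 17%.
- Enhanced v basic among the re-randomised: D = 2.80 × √(2/193.5) = 0.285.

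**The case against.** The strongest reply is that the plan means the initial arm. Aim 1 is headed TCBD against usual care, 6.1 opens with control and TCBD as its example and mentions an initial dichotomy, the description of the enhanced group says those caregivers stay in the intervention arm, 6.2 promises intention-to-treat, and a single coefficient suits two groups better than three. On that reading, naming basic and enhanced merely lists who is in the TCBD arm, and there is no bias. This reading is available. But intention-to-treat does not settle the matter when there are two randomisations, and every detectable effect in 6.1 is for basic or enhanced separately. The initial-arm reading therefore exchanges a biased contrast for one without stated power.

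6.1 introduces its group-size simulation as being for Aim 2. The detectable effects that follow are nevertheless for the binary outcome and CPaSS, which are Aim 1 outcomes, and trajectory power has its own text afterwards.

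Three limits stand. The group composition is inferred from rounded figures, not stated. The largest error rates come from unadjusted tests, and the adjusted ones are lower. The joint Month-6 and Month-12 GLMM was not simulated. The effective n of 295 is also mildly conservative: it ignores that Month-6 status explains some of the Month-12 variation.

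**Conclusion.** The concern holds, and the plan is wrong as written. The contrasts powered in 6.1 compare groups selected on an earlier value of the outcome with unselected controls, and 6.2 does not rule them out as the primary analysis. With nothing working and persistence of 30–70%, unadjusted tests give a false benefit of basic in about 8–55% of trials and a false harm of enhanced in about 11–95%. With baseline adjustment and persistence of 30–54%, the figures are about 6–29% and 9–60%. The size depends on persistence and on how well baseline predicts follow-up, neither of which is in the documents. The direction needs only a positive association between Month-6 and Month-12 use; with none, the error rates are nominal. The pooled initial-arm contrast is sound, but its power for the plan's own rates is about 64%, below the 80% that 6.1 works to.

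**What to change.** In 6.2:

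1. Define the primary Aim 1 indicator as initially randomised TCBD v control.
2. If basic and enhanced are to be compared with control, estimate the two embedded strategies in place of the raw groups: basic throughout, and basic followed by enhanced if restraint use is not size-appropriate at Month 6. Month-6 responders take weight 1 and count in both strategies; re-randomised caregivers take weight 2 in the strategy they followed. Use robust standard errors. State that TCBD caregivers never re-randomised, including those without a Month-6 assessment, take weight 1.
3. Compare enhanced with basic only among the re-randomised.
4. Use the initial arm or the same weights where treatment group enters the Aim 2 multinomial model and any cost-effectiveness ratio based on size-appropriate use.

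In 6.1, restate the detectable effects for these contrasts. At 516/204 they are about 26.7% v 17% (D 0.23) for pooled TCBD, about 27.7% v 17% (D 0.26) for each strategy, and D about 0.28 for enhanced v basic among the re-randomised. The strategy figure is slightly worse than the 0.25 now stated for basic and better than the 0.28 stated for enhanced. The restatement should also settle the allocation: 204/516 is not the 3:1 of 3.2, and on 180/540 the power for 25% v 17% is about 61%.

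The cost is SAP rewording, a weighted GLM, and disclosure of the 64% power for the plan's own assumption. No new data or procedures are needed.

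### The primary CPaSS model names no variance estimator that allows for unequal spread between arms, so with 3:1 allocation its standard error may be wrong in either direction

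*Combined protocol and SAP*

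**What the plan says.** CPaSS is one of two primary outcomes. Section 6.2 (Aim 1) states that "for numeric outcomes (CPaSS-D) we will initially specify linear (Gaussian) GLM(M)s; this choice will be scrutinized by analyzing model diagnostics". It takes the treatment-group coefficient as the inferential target and likens the analysis to ANCOVA. On the significance level it says "All statistical hypothesis tests and power calculations will use a two-sided = 0.05". No robust, Welch-type or arm-specific variance is named for CPaSS. Bootstrapping appears only for the cost measures, in the exploratory part of section 6.1.

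Section 3.2 uses block randomization "to assign eligible caregivers to the TCBD intervention or control group in a 3:1 ratio". Section 4.2 plans to "recruit 900 caregivers who will be enrolled in the study and randomized to intervention or control". Section 6.1 assumes that "only 80% of the target sample (n=204 controls and n=516 TCBD in the initial dichotomy) will be available for analysis at follow-up", which is 516/204 = 2.53:1. It gives detectable standardized CPaSS differences of 0.25 for basic TCBD versus control and 0.28 for enhanced TCBD versus control. It gives no CPaSS standard deviation, and for the Aim 2 simulation it concedes that the score's variability is unknown.

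**The concern.** A Gaussian linear model with a single residual variance estimates that variance mostly from the larger arm, while the true uncertainty of a difference in means comes mostly from the smaller arm. With equal arms the two effects cancel. With about three TCBD caregivers per control they do not. If control scores vary more, the model's standard error is too small and the test rejects too often. If TCBD scores vary more, it is too large and power is lost.

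Unequal spread is plausible here. Section 6.1 expects 25% of TCBD caregivers to reach size-appropriate use by Month 6, and Aim 2 expects at least four response patterns. By Month 12 the TCBD arm mixes responders, continued basic and enhanced caregivers, and the control arm has no such split. At stake is whether the confidence interval and p-value for a primary outcome have their nominal properties.

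**Working it through.** **Inputs.** Two-sided 5% (6.2). Control 204 and TCBD 516 (6.1). At a strict 3:1, 80% of 900 is 720, or 180:540 (4.2, 3.2). In 6.1, 75% of TCBD are re-randomized, and 3.2 makes that 1:1. So enhanced = 516 × 0.75/2 = 193.5, and basic = 516 − 193.5 = 322.5. SD ratios are assumed, because the documents give none.

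**Step 1: the plan's own figures.** Detectable D = (1.96 + 0.84) × √(1/n₀ + 1/n₁), using unrounded normal quantiles.
- Basic versus control, 322.5 v 204: 0.2506, against 0.25 stated.
- Enhanced versus control, 193.5 v 204: 0.2811, against 0.28 stated.

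Both reproduce, and both assume equal SDs.

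**Step 2: error of a nominal 5% single-variance test when means are equal but spreads differ.**
- True variance: T = s₁²/n₁ + s₀²/n₀.
- Model variance: M = [(n₁s₁² + n₀s₀²)/(n₁ + n₀)] × (1/n₁ + 1/n₀).
- Actual error: 2Φ(−1.96 × √(M/T)).

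Example at 204:516 with control SD 1.2 times TCBD. The pooled variance is (516 + 204 × 1.44)/720 = 1.125. M = 0.00769, T = 0.00900, √(M/T) = 0.925, and the error is 7.0%.

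| Comparison (control : TCBD) | Control SD ×1.2 | Control SD ×1.3 | TCBD SD ×1.2 | TCBD SD ×1.3 |
|---|---|---|---|---|
| All TCBD, 204:516 | 7.0% | 8.0% | 3.4% | 2.8% |
| All TCBD, 180:540 | 7.3% | 8.5% | 3.2% | 2.6% |
| Basic alone, 204:322.5 | 6.0% | 6.4% | 4.1% | 3.8% |
| Enhanced alone, 204:193.5 | 4.9% | 4.8% | 5.1% | 5.2% |
| Equal arms, 360:360 | 5.0% | 5.0% | 5.0% | 5.0% |

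**Step 3: an effect confined to a share q of TCBD caregivers.** Take an overall D of 0.25 in control-SD units. If the gain δ = 0.25/q is unrelated to the untreated score, TCBD variance is 1 + q(1 − q)δ².
- q = 25%: δ = 1.0, variance 1.1875, SD ratio 1.09. At 180:540 the model SE is 0.0919 against a true 0.0881, 4% too large. Power is Φ(0.25/0.0881 − 1.96 × 1.044) = 78.6%, against 81.0% with a correct SE. At 204:516 it is 81.9% against 83.8%.
- q = 10.6% (27.6% − 17%, the detectable gap for basic TCBD in 6.1): δ = 2.36, SD ratio 1.24. For all TCBD the model SE is 11% too large and power 71% against 78% at 180:540, or 9.5% and 75% against 80.5% at 204:516. For basic versus control alone, the comparison to which 6.1 attaches D = 0.25, it is 4.8% and 69% against 72%.
- If the same overall gain falls only on the lowest-scoring 25%, TCBD spread shrinks instead (SD ratio 0.74). A 95% interval for all TCBD versus control then misses 8.4% of the time at 204:516 and 9.0% at 180:540.

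**Step 4: does a robust SE cure it?** A baseline-adjusted ANCOVA was simulated with 5,000 runs per cell, an assumed baseline correlation of 0.5 and SD ratios (TCBD/control) from 0.67 to 1.5. The single-variance test rejected 1.9% to 9.7% of the time at 204:516 and 1.6% to 10.6% at 180:540. With HC2 standard errors the range was 4.5% to 5.2% over both splits. With equal spreads HC2 gave 5.1% at both.

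**The case against.** Four things can fairly be said on the other side.

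**The SD ratios are assumed.** This stands. A reader might infer that the CPaSS intervals will fail to cover at 95%; the documents do not support that, because they give no CPaSS SD. Their only variance assumption, variance equal to the mean in the Aim 2 simulation, gives an SD ratio of only 1.03 to 1.05 and an error of 4.4% to 4.7% at 180:540 (4.5% to 4.7% at 204:516), for D = 0.25 and assumed control means of 5 to 20. CPaSS also scores seating position, fit and misuse, and TCBD caregivers get messages about non-critical errors. Gains therefore need not be confined to those who change restraint.

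**The larger figures need a pooled contrast.** This also stands. Section 6.1 powers basic and enhanced TCBD separately against control. Fitted as separate two-group comparisons, the first is moderately exposed and the second barely. However, 6.2 targets a treatment-group coefficient without saying how the groups are coded, and a joint model shares one variance.

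**There is no route to false positives under a true null.** A reader might infer that a partial TCBD effect inflates type I error. It does not: if TCBD affects nobody, randomized arms share one distribution and this mechanism creates no unequal spread. The documents give no other reason for control to vary more when means are equal.

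**Diagnostics are promised.** Residual spread by arm is a routine check, so this is partial cover. The clause names no trigger and no replacement variance. A reader might go further and ask that the linear model stay primary whatever the diagnostics show. That is a separate and more debatable question of pre-specification, and this point does not need it.

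**Conclusion.** The point holds in a conditional form. As written, the CPaSS analysis defaults to one residual variance under unequal allocation, and nothing in the plan supports equal variances. The direction of any error is unknown: gains unrelated to the untreated score widen TCBD spread, while gains among low scorers narrow it.

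The size depends on the contrast and on assumed SD ratios. For all TCBD versus control, or a shared-variance model, a 20% to 30% difference in SD moves a nominal 5% error to between about 3% and 8%. For basic versus control alone the range is about 4% to 6%, and for enhanced versus control alone the change is negligible. If a quarter of caregivers benefit independently of their score, the cost is about two percentage points of power. This is worth correcting because the remedy is cheap, not because serious distortion has been shown.

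**What to change.** Add one sentence to section 6.2: the CPaSS treatment contrast uses heteroscedasticity-robust (HC2 or HC3) standard errors in the single-time-point linear model, and robust standard errors or arm-specific residual variances in the mixed model.

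Design, data collection and sample size are unchanged. The downside is a negligible loss of precision if the variances turn out to be equal.
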